5.2 Secondary outcomes

Clinical data will be collected using the following questionnaires:

1. Neck Disability Index (NDI)

2. Numerical rating scale of pain scale (0-10)
3. 13-item Tampa Scale of Kinesiophobia (TSK- 13)
4. Pain Catastrophising Scale (PCS)
5. EQ-5D-5L (EuroQol)
6. STarT MSK Screening Tool

5.2.1 Pain and function

The Neck Disability Index (NDI) is a self-report questionnaire used to determine how neck pain affects a patient's daily life and to assess the self-rated disability of patients with neck pain. The NDI consists of ten questions in the following domains: Pain Intensity, Personal Care, Lifting, Reading, Headaches, Concentration, Work, Driving, Sleeping, and Recreation.

Scoring: Each question contains six answer choices, scored from 0 (no disability) to 5 (complete disability). All section scores are then totaled. Scoring is reported on a 0-50 scale, 0 being the best possible score and 50 being the worst. Alternately, the score can be reported from 0-100. The score is often reported as a percentage (0-100%).

The numerical rating scale is a scale designed to help assess the extent of an individual's pain. The NRS consists of a numeric version of the visual analog scale. The most common form of the NRS is a horizontal line with an eleven point numeric range. It is labeled from zero to ten, with zero being an example of someone with no pain and ten being the worst pain possible. This type of scale can be administered verbally. It can also be administered via paper to be completed physically.

5.2.2 Catastrophising

The Pain Catastrophising Scale has 13 items rated on the Likert scale of 0='Not at all', 1='To a slight degree', 2='To a moderate degree', 3='To a great degree', and 4='All the time', such that a higher score indicates a higher level of catastrophizing. Items can be summed to produce three subscales (Helplessness [PCS-H] items 1, 2, 3, 4, 5 and 12; Magnification [PCS-M] items 6, 7 and 13; and Rumination [PCS-R] items 8, 9, 10 and 11) and a total score (sum of three subscales, range 0-52). If there are up to two missing items across the whole scale, these can be replaced by the mean of the completed items, and then the subscale and total scores calculated (3) Otherwise, scores can only be completed where there are no missing items within a subscale. A total score of 30 indicates a clinically relevant level of catastrophizing.

5.2.3 Kinesiophobia

The Tampa Scale of Kinesiophobia is a 13-item questionnaire evaluating fear of movement, fear of physical activity, and fear avoidance. Items are scored ‘strongly agree’, ‘disagree’, ‘agree’ and ‘strongly agree’. For questions 1, 2, 3, 5, 6, 7, 9, 10, 11, 13 the responses range from 1-4 respectively.

The total score of the scale ranges from 17-52 and the score is calculated by adding up the responses to all items (up to two missing items can be replaced by the mean of the other completed items, otherwise the instrument is invalid). A total score of more than 37 indicates presence of kinesiophobia.

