5.3.7 Musculoskeletal Patient Reported Experience Measure

A patient reported experience measure will be completed at 14 weeks. This self- administered questionnaire asks about patient's experiences of undergoing an intervention for their condition. Questions 1-12 focus on satisfaction, being involved in decisions, feeling listened

to, explanations, time, care, confidence, review opportunities, information, care coordination, needs, guidance. Questions 1-12 have 3 levels of responses for each domain (3= yes, definitely, 2= yes to some extent, 1= no not at all. Question 13 has five levels of responses for each domain (5= extremely, 4= very, 3= moderately, 2= slightly, 1= not at all. Question 14 has five levels of responses (5= very good, 4= good, 3= neither good nor poor, 2= very poor, 1= don't know.

Follow-up

Participants in both arms will complete all secondary outcomes at baseline, 14 weeks and 6 months post-randomisation.

6. Data

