Appendix C: Recruitment and retention summary tables

Table 2: Recruitment log

Site	Number Identified and sent PIS by CRN	Number contacted and screened (95% CI)	Number Consenting (95% CI)	Number Randomised (95% CI)	Number Withdrawn (95% CI)
Total					

Table 3: Withdrawal's log

Site	Participant ID	Reason for Withdrawal

Table 4: Summary of outcomes by treatment group and time point

Continuous outcome measures, N, mean (SD)	14 weeks			6 months		
	Intervention (n=x)	Control (n=x)	Overall (n=)	Intervention (n=x)	Control (n=x)	Overall (n=)
WOMAC Pain subscale						
PCS-H subscale						

PCS-M subscale						
PCS-R subscale						
PCS total score						
Tampa scale						
EQ-5D-5L index value score						
EQ-5D-5L VAS						
Categorical outcome measures, n (%)						
PCS total score ≥ 30						
Tampa scale >37						
Severe (20- 24)						

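### The scoring text for the 13-item Tampa scale is wrong or incomplete (range, response label, three items, unsourced cut-off), and question 14 of the patient experience measure codes a non-answer below the worst rating

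*SAP*

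**What the plan says.** **Tampa scale (SAP section 5.2.3).** The instrument is defined by its length: "The Tampa Scale of Kinesiophobia is a 13-item questionnaire evaluating fear of movement, fear of physical activity, and fear avoidance". The response labels are given as "Items are scored ‘strongly agree’, ‘disagree’, ‘agree’ and ‘strongly agree", so the first and the last are the same. The item scores follow: "For questions 1, 2, 3, 5, 6, 7, 9, 10, 11, 13 the responses range from 1-4 respectively". Items 4, 8 and 12 are not in that list, and nothing else in the SAP scores them. The total is then defined: "The total score of the scale ranges from 17-52 and the score is calculated by adding up the responses to all items". Where one or two responses are missing, the section allows the mean of the completed ones in their place. It also adds a threshold without a reference: "A total score of more than 37 indicates presence of kinesiophobia".

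The total is reported as N, mean (SD) at baseline (Appendix A, Table 1) and at follow-up (Appendix C, Table 4). Table 4 also has a categorical row, "Tampa scale >37".

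**Patient experience measure (SAP section 5.3.7).** Question 14 is said to have five response levels, coded "5= very good, 4= good, 3= neither good nor poor, 2= very poor". The same sentence goes on to give the code 1 to *don't know*. No level called *poor* appears. Appendix A, Table 3 gives the measure one blank row by arm and names no statistic.

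**The concern.** A SAP should let two analysts working apart obtain the same score from the same answers. Section 5.2.3 does not. The stated range cannot come from the stated instrument, one answer is attached to both 1 and 4, and three of the thirteen items have no rule although they are summed. The threshold stands beside a range that does not fit, with no source by which to check it.

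Section 5.1 lists the standard deviations of outcome measures among the parameters this trial is meant to supply for the main trial's sample size, and section 4.2 makes the suitability of the outcome measures an objective. An uncertain item rule affects the mean, the SD and the percentage above 37 together.

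On question 14, a participant who offers no opinion is given a lower number than one who reports the worst experience. If those numbers are used as a score, the result is biased downwards by people who made no complaint.

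**Working it through.** **Inputs.** Number of Tampa items k = 13 (sections 5.2 and 5.2.3). Item scores 1 to 4, stated for ten items (5.2.3). Stated total range 17 to 52 (5.2.3). Cut-off above 37 (5.2.3 and Appendix C, Table 4). Question 14 codes 5, 4, 3, 2, 1 (5.3.7).

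**1. Range of the total.** A sum of k items scored 1 to 4 runs from k × 1 to k × 4.
- 13 items: 13 × 1 = 13 and 13 × 4 = 52. The plan's upper bound is reproduced; its lower bound is not.
- Items 4, 8 and 12 reversed: a reversed item still runs from 1 to 4, so the range stays 13 to 52.
- The ten listed items only: 10 to 40.
- Two missing items replaced by the mean of the other eleven: 11 × 13/11 = 13 and 44 × 13/11 = 52, again 13 to 52.
- A floor of 17 would need the three unlisted items to contribute at least 17 − 10 = 7. Three items with a minimum of 1 each can contribute as little as 3.

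None of these gives 17 to 52.

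**2. Effect of the missing rule for three items.** If x is the forward score of an item, its reversed score is 5 − x. The two differ by |2x − 5|, which is 3 when x is 1 or 4. Over three items the largest difference is 3 × 3 = 9 points, or 9/39 = 23% of the 39-point range (52 − 13).

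The choice can also change the category. A participant scoring 3 on every item before any reversal totals 13 × 3 = 39 if all items are scored forwards, which is above 37. With items 4, 8 and 12 reversed the total is 10 × 3 + 3 × (5 − 3) = 36, which is not.

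**3. Response label.** Four labels matched in order to 1, 2, 3, 4 put *strongly agree* at both 1 and 4. Read literally, that answer has two scores.

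**4. Position of the cut-off.** On 13 to 52, a total of 37 lies (37 − 13)/39 = 62% of the way up. On the stated 17 to 52 it lies (37 − 17)/35 = 57% up. This shows only that the threshold's meaning depends on the range. It does not show which value is right.

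**5. Question 14.** If n ratings have mean m and d further participants answer *don't know* coded 1, the mean falls by d(m − 1)/(n + d). As an illustration with assumed answers, take 16 ratings: 6 very good, 8 good and 2 in the middle category. Their mean is (30 + 32 + 6)/16 = 4.25.
- d = 1: (68 + 1)/17 = 4.06, a fall of 0.19.
- d = 3: (68 + 3)/19 = 3.74, a fall of 0.51.

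Nobody in the example gave a rating below the middle category. If question 14 is instead tabulated as number and percentage per category, the codes are only labels and the fall is zero.

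**The case against.** The strongest reply is that most of this is drafting. The range sentence is descriptive and the rule is the sum, so a misstated minimum changes no computed total. The SAP describes no range check that would reject totals of 13 to 16. The order of the middle labels also makes the intended first label fairly clear. All of that stands, and it limits the weight of the range and label errors. It does not answer the missing rule for items 4, 8 and 12, which does change totals. A reader might take their omission to mean that they are reverse-scored, but the document does not say so.

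A reader might also infer that the floor of 17 shows text carried over from a 17-item version (17 to 68), that 37 is therefore wrong for 13 items, and that participants below it are misclassified. The SAP does not support this. It never mentions a 17-item version, and a typing error would explain the floor equally well. Rescaling 37 to a shorter form would further assume that cut-offs convert in proportion to length. No score distribution is given from which to count anyone misclassified. What can be said is that the cut-off is unsourced.

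On question 14, a reader might conclude that non-answers will be counted as the worst experience. That holds only if the codes are averaged or ranked. The SAP defines no total or mean for this measure, and section 10.2 summarises categorical variables as number and percentage.

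Finally, section 10.4 plans no formal hypothesis tests and takes its effectiveness signal from the Neck Disability Index. The quantitative stop-go criteria in section 4.2 use recruitment, attendance and data return. That stands too.

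**Conclusion.** The point holds in limited form and should be corrected before scoring. It is certain from the text that the Tampa lower bound should be 13, that one label is duplicated, and that three summed items lack a rule. The last matters most, at up to 9 points per participant. That figure is the extreme case; the shift is smaller for other response patterns and zero if the fielded form scores all items in one direction and the analyst does so.

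The cut-off above 37 is unsupported, not shown to be wrong. The coding of question 14 is mis-ordered as written, and its harm is conditional on the codes being used as numbers. The falls of 0.19 and 0.51 are illustrations on assumed answers.

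The effect is confined to descriptive summaries of the Tampa scale and the experience measure, and to the Tampa SD if it is used to plan the main trial. The stop-go criteria and this trial's sample size are unaffected.

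**What to change.** In section 5.2.3:
- state the range as 13 to 52;
- correct the duplicated response label against the questionnaire as fielded;
- state the scoring direction of items 4, 8 and 12 for that version, and apply any reversal before missing items are replaced by the mean;
- cite a source for the cut-off above 37 that applies to the 13-item form, or delete the sentence and the matching row of Appendix C, Table 4. Mean (SD) is already planned, so dropping the row leaves the main summary intact.

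In section 5.3.7:
- treat *don't know* on question 14 as a non-rating and report it as a separate count;
- order the remaining categories;
- check whether the fielded form offers *poor*, and add that level if it does;
- name the statistic for Appendix A, Table 3.

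The cost is SAP wording and a recode in the analysis script, with at most one dichotomised row lost. No data need be collected again, provided item-level responses have been kept.

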5.2.4 Risk of chronicity

The STarT MSK tool aims to ensure that patients with common musculoskeletal conditions receive the right treatments at the earliest opportunity. The tool contains 10 items that once scored can place patients into three categories based on their risk of a poor outcome (low, medium, and high). The Keele STarT MSK Tool has 10 items that ask about predictors of poor outcomes for a range of conditions. The items ask about the function and disability, pain and coping, comorbidity and the impact of pain. There is a visual analogue scale (VAS), which records participants’ overall evaluation of their pain from 0 ‘no pain’ to 10 ‘pain as bad as it could be’. This followed by 9 questions with ‘yes’ or ‘no’ responses. A total maximum score is 12.0-4 represents low risk, 5-8 medium risk and 9-12 high risk of chronicity.

5.2.5 Health-related quality of life

The EQ-5D™ (4) is a widely used self-reported generic measure of HRQoL which comprises two parts: the classification of 5 dimensions of health (mobility, self-care, usual activities, pain/discomfort, and anxiety/depression) and a visual analogue scale (VAS), which records participants’ overall evaluation of their health on a scale from 0 (worst imaginable health) to 100 (best imaginable health). The EQ-5D has been validated in many different patient populations including diabetes, cardiovascular problems, chronic obstructive pulmonary disease, cancer, chronic pain, and rheumatoid arthritis.

The EQ-5D-5L has five levels of responses for each domain (1 = no problems, 2 = slight problems, 3 = moderate problems, 4 = severe problems, and 5 = unable to do/extreme problems), which lead to 3125 unique combinations of health states where each health state is mapped to a utility index score (the utility values are on a scale where negative values correspond to a state worse than death, 0 corresponds to a health state equivalent to being dead

and 1 corresponds to perfect health) by making use of a valuation set. Participants who die can be given a score of 0 for any assessment time point following their date of death. There is a valuation set for the EQ-5D-5L available for England (5); however, this is currently under revision. Meanwhile, the UK's National Institute for Health and Care Excellence (NICE) recommends that utility values should be calculated using the crosswalk developed by van Hout et al (6). Utility scores will be calculated following the NICE guidance at the time of the analysis and detailed in the final report.

5.3 Other collected variables

5.3.1 Baseline demographics

Age, gender, height and weight (which will be used to calculate BMI) will be recorded at baseline.

5.3.2 Trial retention

The proportion of withdrawals and the proportion of completed 6-month questionnaires will be used to determine trial retention. Withdrawals and losses to follow up will be classified as:

- Participant withdrawn from follow-up only
- Participant withdrawn from the intervention but agrees to further follow-up
- Participants fully withdrawn from the intervention and follow up
- Participants lost to follow-up
- Participant has died

5.3.3 Intervention adherence

The number of participants attending clinical sessions will be monitored at each site throughout the trial. The intervention consists of up to 7 sessions.

5.3.4 Intervention fidelity

The PiP arm will be monitored for fidelity through the review of clinical notes.

Step 2- Consistency of fidelity check between two raters

- Same set of five notes will be analysed by both raters.
- Following this, the scoring will be compared for consistency, aiming for a cohens kappa score of 0.7 . If above 0.7, ok to continue to step 3. If below 0.7, discussion to clarify areas of inconsistency.
- Following this, an additional set of five notes checked. Consistency scored with cohens kappa. If continues below 0.7, consider change of methods, fidelity assessment structure or processes. Repeat stage 1 and 2. If above 0.7, continue to step 3

Step 3- intra tester reliability

- Same set of five notes analysed again 2 weeks later.

- Intraclass Correlation Coefficient (ICC) calculated. If above 0.75, ok to continue to step 4. If below 0.75. Repeated 1 week later.
- If repeated test below 0.75, review understanding of checklist and processes.
- Repeat 1 week later, if below 0.75, repeat step 1.

Step 4- stratified sampling of participants into red (2 sets) /amber (3 sets) /green participants (4 or 5 sets)

- Participants stratified into red/ amber/ green.
- Once stratified, participants randomly sampled for fidelity assessment using Microsoft excel. Aiming for 4 green= 16-20 notes, 4 amber= 12 notes and 4 red participants= 8 notes. Maximum sets of notes = 40 notes + 10 pilot notes= 50 sets of notes.
- Participants then randomly allocated to rater 1 and rater 2 aiming for even distribution of red/amber/green participants.

Step 5- Assessments analysed

- Descriptive analysis of scores broken down into tester and red/amber/green categories. Mean (SD) scores presented.
- Kappa score for inter tester
- ICC for intra tester

5.3.5 Adverse events

Adverse events will be reported throughout the 6 month follow up period. The trial physiotherapists and participants are responsible for notifying the research team about adverse events. Adverse events related to CMT will be assessed for seriousness, expectedness and relatedness by the chief investigator and principal investigator. The 'NIHR- Decision Tree for Adverse Event Reporting- NON CTIMPS' will be used to guide this assessment. All adverse events will be recorded by the research trial coordinator. Any related or serious adverse events will be reported to the Research Ethics Committee by the chief investigator. Adverse events will be included in regular progress reports to the steering group committee.

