This analysis plan was written prior to the completion of recruitment and was prepared according to UoS SOPs and guidance documents.

2. Definition of terms/acronyms

AE	Adverse event
CONSORT	Consolidated standards of reporting trials
CMT	Cognitive muscular therapy
NIHR	National Institute of Health Research
CTIMP	Clinical trial of Investigational Medicinal Product
RCT	Randomised controlled trial.
SAE	Serious adverse event
SAP	Statistical analysis plan

3. Design

This study is an open, multi-centred, two-armed feasibility, randomised trial with allocation at the patient level, with embedded health economic and qualitative evaluations (not detailed further in this SAP). The two arms are: cognitive muscular therapy (CMT) and psychologically informed physiotherapy

Full details of the background and design of the trial are presented in the protocol (Protocol-(COMPIN)- v5 (17-04-24).docx)

4. Trial objectives

This trial aims to deliver key parameters that are required to run a future, pragmatic, two-arm RCT.

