10.7 Adverse events

Adverse events and serious adverse events will be presented by trial arm and site, itemised with descriptions (Appendix E).

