Appendix D: Notes audit log

Appendix E: Adverse events

ID	Description	Severity	Action taken	Outcome	Allocation

Adverse events	Intervention	Control	Total

	(N =)	(N =)	(N =)
Serious Adverse Events N (%)			
Relatedness			
Related			
Unrelated			
Expectedness			
Expected			
Unexpected			
Non-Serious Adverse Events N (%)			
Grading			
Mild			
Moderate			
Severe			
Relatedness			
Related			
Unrelated			
Expectedness			
Expected			
Unexpected

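### SAP section 5.3.5 limits the assessment of adverse events to those related to CMT, which contradicts its own ethics-reporting rule, section 10.7 and the two-arm table in Appendix E

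*SAP*

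**What the plan says.** Five statements in the SAP bear on the point.

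- Section 3 describes two treated arms: "The two arms are: cognitive muscular therapy (CMT) and psychologically informed physiotherapy". The comparator is therefore an active treatment with its own sessions (section 10.5 counts five for PiP).
- Section 5.3.5, on recording: "All adverse events will be recorded by the research trial coordinator". There is no limit by arm.
- Section 5.3.5, on assessment: "Adverse events related to CMT will be assessed for seriousness, expectedness and relatedness by the chief investigator and principal investigator". The NIHR decision tree named next is there to guide this same assessment.
- Section 5.3.5, on reporting: "Any related or serious adverse events will be reported to the Research Ethics Committee by the chief investigator". Again there is no limit by arm.
- Section 10.7, on presentation: "Adverse events and serious adverse events will be presented by trial arm and site". It refers to Appendix E, whose summary table has Intervention, Control and Total columns under two main headings, "Serious Adverse Events N" and "Non-Serious Adverse Events N". Each heading is split into Related and Unrelated and into Expected and Unexpected. Non-serious events are also graded.

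**The concern.** The sentence on assessment is narrower than everything that depends on it. An event has to be regarded as related to CMT before its relatedness is assessed, and the SAP does not say who makes that first judgement or by what standard. The trial is open, so it would be made with the allocation known. Events in the PiP arm have no stated route to assessment at all.

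Two things are at stake. A serious event in the PiP arm, or a serious CMT-arm event not at first attributed to CMT, has no stated step at which it is classified as serious, although ethics reporting depends on that classification. And the by-arm safety summary would compare a column built from assessed events with one for which the SAP provides no assessment.

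**Working it through.** The SAP gives no figure for adverse events, so the check is a comparison of provisions. For each kind of event, the table shows what the SAP provides and what its later steps need.

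| Kind of event | Recorded (5.3.5) | Assessed (5.3.5) | Classification needed for ethics reporting (5.3.5) | Classification needed for Appendix E |
|---|---|---|---|---|
| CMT arm, first attributed to CMT | yes | yes | yes | yes |
| CMT arm, not first attributed to CMT | yes | no provision | yes | yes |
| PiP arm | yes | no provision | yes | yes |

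The last two columns follow from these steps:

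1. *Ethics reporting.* To report every related or serious event, seriousness and relatedness must be known for every event, whatever the arm.
2. *Summary table.* Every row lies under the serious or the non-serious heading, including the grading rows. An event whose seriousness has not been assessed has no valid cell. Control can be filled only if PiP events are assessed.
3. *Unrelated rows.* An event first attributed to CMT may be judged unrelated by the investigators, and would then be counted there. CMT-arm events never attributed to CMT, and all PiP events, would not reach those rows under the written rule. The rows would be incomplete, not necessarily empty.
4. *Line listing.* Appendix E also lists events with description, severity, action taken, outcome and allocation. PiP events would appear there, so event capture is not affected. The listing has no columns for seriousness, relatedness or expectedness and so cannot supply the missing classification.

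**Scale, under assumptions only.** Section 7 plans 48 participants and, after 20% dropout, about 19 per group. This reproduces: 48 × (1 − 0.20) / 2 = 19.2. Equal allocation then means 48 / 2 = 24 randomised per arm. Assume that the same proportion of participants in each arm has an event needing classification, from 5% to 20%:

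- Expected participants per arm: 24 × 0.05 = 1.2 to 24 × 0.20 = 4.8.
- CMT arm, if 25% to 100% of these are first attributed to CMT: 1.2 × 0.25 = 0.3 to 4.8 × 1.00 = 4.8 classified.
- PiP arm: none classified under the written rule, so 1.2 to 4.8 are left unclassified.

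These rates are not in the SAP. The range shows only that the numbers are small and that the difference in classification arises from the rule, not from any difference between treatments.

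**The case against.** The strongest reply is that this is loose drafting in one sentence. Every other provision points to both arms: all events are recorded, the reporting sentence has no limit by arm, and the summary table has a Control column. Physiotherapists and participants notify events first and the investigators assess them afterwards, so *related to CMT* may simply mean suspected to be related, which removes the circularity. The protocol, which is not at hand, may set out the full procedure. No stop-go criterion in section 4.2 uses safety, section 10.4 rules out formal testing of outcomes between groups, and the safety summary is descriptive.

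Most of this stands, and it limits the point in three ways.

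- A reader might infer that PiP events will go unassessed and that the safety table is biased by construction. The SAP does not establish that. Its other provisions suggest the opposite intention.
- A reader might infer that the Unrelated rows can never be filled. An event first suspected of being related to CMT can be judged unrelated, so this is wrong for the CMT arm.
- A reader might infer a false excess of events under CMT, for example 24 × 0.10 = 2.4 against 0. That rests on one assumed rate and on counting unassessed PiP events as zero. Nothing in the SAP says they would be. A blank or unclassified cell, visible against the line listing, is at least as likely.

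The reply does not remove the contradiction. Even if *related* is read as *suspected to be related*, PiP events and CMT-arm events that nobody suspects remain outside the rule, while ethics reporting and Appendix E need them classified. What was probably intended does not replace a written rule that says something else.

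**Conclusion.** The point holds as an internal contradiction. The assessment rule in section 5.3.5 covers a subset of CMT-related events, while the reporting sentence in that section, the presentation in section 10.7 and the table in Appendix E all need every event in both arms to be classified. If the rule is followed literally, classification differs by arm, the Control column cannot be validly filled, and the Unrelated rows are incomplete. Recording and listing of events are unaffected.

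The size cannot be derived from the SAP. The conclusion rests on its wording alone and needs no event rate. It does not show that PiP events will in practice be left unassessed. No stated progression criterion depends on these rows, so the consequence lies in safety classification and ethics reporting, not in the feasibility decision.

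**What to change.** Reword the assessment sentence in section 5.3.5, for example: *All adverse events in both arms will be assessed for seriousness, relatedness to the allocated intervention (CMT or PiP) or trial procedures, and expectedness.* State that the same assessors and the same procedure apply in each arm. Apply the rule to events already logged before the Appendix E tables are produced, and check that the protocol's safety section agrees.

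The cost is one sentence, plus assessment of a small number of additional events by the same investigators. No change to data capture or to the layout of the summary table is needed.
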